5. AGENT ADMINISTRATION

Intervention will be administered on an outpatient basis. Reported AEs and potential risks are described in Section 6.2.

5.1 Dose Regimen and Dose Groups

The study drug 9cUAB30 240 mg (3 capsules of 80 mg) or *160 mg (2 capsules of 80 mg) will be taken daily for a period of at least 14 days but not to exceed 28 days.

*Depending on if interim dose modification rules are met.

5.2 9cUAB30 Administration

All study drug will be dispensed by research pharmacies at the participating organizations. Three bottles (30 capsules per bottle) will be distributed to study participants at the 240mg dose level. If the interim dose modification rules are met and the study is modified to 160mg daily, two bottles (30 capsules per bottle) will be distributed to the remaining participants. Individually labeled participant-specific bottles of 9cUAB30 will be distributed to the investigational pharmacy at each site. The daily dose will be self-administered at approximately the same time every evening on empty stomach (2 hours after eating and wait for 1 hour before eating again). The last dose will be the day before surgery.

5.3 Run-in Procedures

Not applicable

5.4 Contraindications

Due to the effects demonstrated in other Rexinoids, the following medications are contraindicated:

- bile acid sequestrants (cholestyramine, colestevam, colestipol)
- ezetimibe
- fibric acids (fenofibrate, gemfibrozil)
- nicotinic acid (niacin)

Because of potential effects on drug metabolism other contraindicated agents are:

- St John's Wort
- oral ketoconazole
- tetracycline
- oral corticosteroids
- CYP2B6 Substrates (Sensitive): Bupropion, cyclophosphamide (Activated to acrolein by CYP2B6), efavirenz, irinotecan, ketamine, promethazine, propofol, selegiline,

All medications listed above should be avoided while participants are taking study agent, they may

resume use on the day of surgery.

Because of potential confounding effects on pharmacokinetics, participants may not take other topical or oral retinoids. These agents are:

- retinol
- Retinal
- tretinoin (Retin-A)
- isotretinoin
- alitretinoin
- etretinate
- acitretin
- Tazarotene
- bexarotene
- Adapalene

For participants who choose to co-enroll in an ¹⁸F-FFNP PET/MRI trial, Day 1 of 9cUAB30 study drug administration must be at least 1 day after the FFNP administration to ensure the AE reporting period for the FFNP trial has concluded.

5.5 Concomitant Medications

All medications (prescription and over-the-counter), vitamin and mineral supplements, and/or herbs taken by the participant will be documented on the concomitant medication CRF and will include: 1) start and stop date, dose and route of administration, and indication. Medications taken for a procedure (e.g., biopsy) should also be included. Medications given in the hospital as part of the standard surgical protocol will not be documented as concomitant medications. However, any medications given to treat an adverse or unexpected event following surgery will be documented.

5.6 Dose Modification

No dose modifications will occur for an individual participant. The study dose may be reduced from 240 mg/day to 160 mg/day if interim dose modification rules are met (see Section 13.9). No other dose modifications will be allowed.

5.7 Adherence/Compliance

Subjects that maintain 90% compliance for the time period beginning day 1 of the trial and ending on the day before surgical intervention will be considered compliant. Compliance will be measured through pill counts conducted by the study coordinator or institutional pharmacy and recorded in the CRF.

6. PHARMACEUTICAL INFORMATION

6.1 9cUAB30 (IND 101,064, NCI, DCP)

This Phase Ib clinical study investigating the biologic effect of a novel retinoid 9- cis-UAB30 (9cUAB30) will be conducted under an IND sponsored by NCI, DCP. 9cUAB30 [8- (3',4'-dihydro-1-(2'H)-naphthalen-1'-ylidene)-3,7-dimethyl-2,4,6-octatrienoic acid], has been synthesized at the University of Alabama ([name]) and is undergoing development through the NCI, DCP RAPID program. This new RXR-selective retinoid is a conformationally- constrained analogue of 9-cis-retinoic acid (9-cis-RA) (Muccio et al. 1998).

Evidence continues to accumulate from in vitro and in vivo studies, as well as from clinical trials, that retinoids have therapeutic effects in several neoplastic diseases. Several RXR agonists (rexinoids) have undergone clinical evaluation as potential chemopreventive compounds. 9cUAB30 is a yellow powder which will be formulated into capsules as subsequently described. Active capsules are size 1, Swedish orange, hard-gelatin capsules containing 80 mg 9cUAB30 plus pregelatinized starch, colloidal silicon dioxide, crospovidone and magnesium stearate. All capsules are manufactured under contract to NCI, DCP, and are packaged in 60 cc white HDPE bottles, 30 capsules per bottle, with 33/400 polypropylene caps.

6.2 Reported Adverse Events and Potential Risks

[figure not shown]
[figure not shown]
Nonclinical PK evaluations show that 9cUAB30 is orally available in mice, rats, and dogs. In mice, plasma 9cUAB30 levels were similar after one and seven days of dosing, indicating no drug accumulation. Increases in the area under the drug concentration curve (AUC) were less than proportional to dose possibly due to an increased rate of clearance (Cl) and decreased half-life ($t_{1/2}$) seen at the same time. In rats, drug levels increased with dose. In dogs, the time to maximal drug concentration (t_{max}) was 2–3.5 hours and $t_{1/2}$ was 2.7–4 hours. *In vitro* metabolic studies suggest that human metabolism may be similar to canine metabolism and differ significantly from murine (rat) metabolism. In isolated human liver microsomes, the major cytochrome P 450 (CYP) isozymes responsible for 9cUAB30 metabolism were CYP2C8, CYP2C9 and CYP2C19; at 10 μ M, 9cUAB30 also induced CYP2B6. A 9cUAB30 glucuronide conjugate can be formed by uridine diphosphate (UDP) glucuronosyltransferase 1A9 (UGT1A9).

9cUAB30 has been evaluated in multiple nonclinical toxicity and safety pharmacology studies sponsored by NCI, DCP. In a 28-day oral toxicity study of 9cUAB30 in rats, target organs were the liver and hematologic system. Dose-dependent increases in liver weight as a percent of brain weight, vacuolation in liver tissue consistent with glycogen deposition, and increased serum aspartate aminotransferase (AST) and alkaline phosphatase (ALP) levels were observed. Hematologic changes included dose-dependent decreases in prothrombin time (PT), increases in fibrinogen, and, at the highest dose (100 mg/kg-bw-day), eosinopenia and neutrophilia. The no observed adverse effect level (NOAEL) was considered to be 3 mg/kg-bw/day. In a 28-day oral toxicity study of 9cUAB30 in female dogs, no treatment-related toxicities were observed even at the highest dose (100 mg/kg-bw/day), which was considered the no observed adverse effect level (NOAEL). In safety pharmacology studies, no cardiac effects were seen in female dogs treated with single doses of 9cUAB30 up to 300 mg/kg-bw/day. Additionally, in a functional observational battery (FOB) study in rats, no effects on central nervous system (CNS) or behavior were seen with single doses of 9cUAB30 up to 100 mg/kg-bw/day. In genotoxicity studies, 9cUAB30 was negative in the *in vivo* mouse bone marrow micronucleus assay and the bacterial reverse mutation test (Ames). In the Chinese hamster ovary (CHO) cell assay, 9cUAB30 did not increase chromosome aberrations or polyploidy after three-hour exposure to low levels of 9cUAB30 in the absence of metabolic activation. However, longer duration (24 hours) in the presence or absence of metabolic activation, or higher doses of 9cUAB30 with metabolic activation, increased chromosome aberrations and polyploidy. Because of variable outcomes and lack of a dose response in the CHO cell assay, 28-day *in vivo* mutagenicity and six-month oncogenicity studies were undertaken in transgenic mice. In the Big Blue *lacI/cII* transgenic mouse mutagenicity study, no dose-related increases in mutation frequency were found in the liver, kidney, or spleen. In addition, 9cUAB30 was not oncogenic in *p53^{+/−}* transgenic mice, and there was no evidence of vitamin A-like toxicity. These results, combined with the negative oncogenicity and mutagenicity data, suggest an acceptable toxicity profile for 9cUAB30.

9cUAB30 has been tested in normal volunteers in a phase 1, first-in-human, open-label, single ascending dose study (UWI06-8-03) and in a 28-day double-blind, placebo-controlled, randomized, multiple ascending dose (MAD) study (under two protocols UWI09-8-02, UWI10-16-01R). In the first study, single doses of 5, 10, and 20 mg 9cUAB30 were well tolerated and orally available, with a t_{max} of 2.2–3.1 hours.

Most adverse events (AEs) were grade 1 in severity; Grade 3 AE's were rare and likely unrelated to study agent. There were no grade 4, or serious AEs (SAEs), and no dropouts. The most common treatment-emergent AE (TEAE) was headache with the first dose and little to no occurrence thereafter raising the possibility of caffeine withdrawal due to fasting as a potential cause. Another common TEAE was grade 1 (1 grade 3 event on day 1 prior to initial dose) hypertension which was more frequently observed with higher doses (see Table 3). Because of this observation, we more closely examined Blood Pressure results throughout the study (see figure 2). Based on absolute BP readings there is no evidence of increased BP during the first 24 hours after their initial dose (data not shown) and no evidence of an increase from baseline through day 36 (figure 2). The increase in numbers of TEAE's implies participants entered the study with borderline hypertension and resultant repeated measurements led to sporadic BP elevations meeting CTCAE requirements across participants and sustained elevations within participants where not seen.

Figure 2:

Systolic Blood Pressure (Change from Baseline), 9CUAB30 Phase I**Diastolic Blood Pressure (Change from Baseline), 9CUAB30 Phase I**

*Median and first and third quartiles are displayed

Other common TEAEs were increased blood chloride, decreased hemoglobin (anemia), and hypercholesterolemia. Rare events such as rash, dry skin, sweating, burping after meals, shaking, temperature of body feeling warmer, were also observed. Interestingly, commonly associated retinoid/rexinoid toxicities were not observed with any frequency or significant grade (skin changes, headache, hyperlipidemia, leukopenia, etc.), supporting the hypothesis that the conformational changes to 9cUAB30 structure as compared to 9cRA result in less toxicity. Our data supports that 9cUAB30 daily dosing of ≤ 240 mg/day for up to 28 days continuously is safe.

Table 3: TEAEs by treatment Reported by \geq Three Subjects in UWI09-8-02, UWI10 16 01R

System Organ Class Preferred Term	0 mg (n=12) n(%)	20 mg (n=8) n(%)	40 mg (n=9) n(%)	80 mg (n=8) n(%)	160 mg (n=9) n(%)	240 mg (n=8) n(%)
Any TEAE	10 (83)	6 (75)	9 (100)	6 (75)	8 (89)	8 (100)
Gastrointestinal Disorders	1 (8)	3 (38)	2 (22)	2 (25)	2 (22)	0 (0)
Nausea	1 (8)	1 (13)	1 (11)	0 (0)	2 (22)	0 (0)
Vomiting	1 (8)	1 (13)	1 (11)	0 (0)	0 (0)	0 (0)
General Disorders and Administrative Site Conditions	1 (8)	3 (38)	0 (0)	1 (13)	2 (22)	0 (0)
Fatigue	0 (0)	2 (25)	0 (0)	0 (0)	2 (22)	0 (0)
Infections and Infestations	5 (42)	0 (0)	0 (0)	2 (25)	2 (22)	2 (25)
Sinusitis	2 (17)	0 (0)	0 (0)	0 (0)	1 (11)	2 (25)
Investigations	4 (33)	1 (13)	5 (56)	2 (25)	2 (22)	5 (63)
Blood Chloride Increased	1 (8)	0 (0)	1 (11)	2 (25)	1 (11)	0 (0)
Cholesterol High	1 (8)	1 (13)	2 (22)	1 (13)	1 (11)	1 (13)
Increased LDL Cholesterol	1 (8)	1 (13)	0 (0)	1 (13)	0 (0)	0 (0)
Metabolism and Nutrition Disorders	3 (25)	2 (25)	2 (22)	3 (38)	1 (11)	0 (0)
Hypertriglyceridemia	2 (17)	2 (25)	2 (22)	2 (25)	1 (11)	0 (0)
Musculoskeletal And Connective Tissue Disorders	1 (8)	1 (13)	0 (0)	1 (13)	1 (11)	4 (50)
Back pain	0 (0)	1 (13)	0 (0)	0 (0)	1 (11)	1 (13)
Nervous System Disorders	4 (33)	2 (25)	3 (33)	3 (38)	3 (33)	4 (50)
Headache	3 (25)	2 (25)	3 (33)	3 (38)	2 (22)	4 (50)
Respiratory, Thoracic, and Mediastinal Disorders	0 (0)	1 (13)	0 (0)	2 (25)	1 (11)	2 (25)
Nasal Congestion	0 (0)	1 (13)	0 (0)	2 (25)	0 (0)	1 (13)
Skin and Subcutaneous Tissue Disorders	1 (8)	1 (13)	0 (0)	3 (38)	4 (44)	4 (50)
Dry Skin	0 (0)	1 (13)	0 (0)	2 (25)	0 (0)	1 (13)
Pruritus	0 (0)	0 (0)	0 (0)	0 (0)	1 (11)	3 (38)

System Organ Class Preferred Term	0 mg (n=12) n(%)	20 mg (n=8) n(%)	40 mg (n=9) n(%)	80 mg (n=8) n(%)	160 mg (n=9) n(%)	240 mg (n=8) n(%)
Rash Acneiform	1 (8)	0 (0)	0 (0)	1 (13)	1 (11)	2 (25)
Vascular Disorders	5 (42)	2 (25)	7 (78)	4 (50)	7 (78)	8 (100)
Hot Flashes	2 (17)	0 (0)	0 (0)	0 (0)	1 (11)	0 (0)
Hypertension	5 (42)	2 (25)	7 (78)	4 (50)	7 (78)	8 (100)

6.3 Availability

9cUAB30 is an investigational agent supplied to investigators by the Division of Cancer Prevention (DCP), NCI. The agent is formulated into 80mg capsules.

6.4 Agent Distribution

Agents will only be released by NCI, DCP after documentation of IRB approval of the DCP-approved protocol and consent is provided to DCP and the collection of all Essential Documents is complete (see DCP website for description of Essential Documents).

DCP guidelines require that the agent be shipped directly to the institution or site where the agent will be prepared and administered. NCI, DCP-supplied agents are requested by Consortium Lead Organization (CLO), University of Wisconsin to be dispatched to Participating Organization (PO) by completing the DCP Clinical Drug Request form (NIH-986) (to include complete shipping contact information) and faxing or mailing the form to the DCP agent repository contractor:

[name]
MRIGlobal
DCP Repository
[name]
North Kansas City, MO 64116
[contact]
[contact]
Emergency [contact]

DCP does not permit the transfer of agents between institutions (unless prior approval from DCP is obtained). DCP does not automatically ship agents; the site must make a request.

6.5 Agent Accountability

The Investigator, or a responsible party designated by the Investigator, must maintain a careful record of the inventory and disposition of all agents received from DCP using the NCI Drug Accountability Record Form (DARF). The Investigator is required to maintain adequate records of receipt, dispensing and final disposition of study agent. Include on receipt record from whom the agent was received and to whom study agent was shipped, date, quantity and batch or lot number. On dispensing record, note quantities and dates study agent was dispensed to and returned by each participant.

DCP requirements for agent accountability and the required forms are available on the DCP website.

6.6 Packaging and Labeling

9cUAB30 capsules will be packaged by NCI, DCP. Each bottle will contain 30 capsules of 80mg 9cUAB30. Two-part labels will be placed on each bottle. One part stays on bottle, and one part goes into the participant chart or other designated research record as a source document. Sites will be responsible for recording the Participant ID (PID) number on the bottle once they are dispensed. The label remaining on the bottle will identify study specific information, such as Study title, DCP protocol number, dosing instructions, recommended storage conditions, the name and address of the distributor, and a caution statement indicating that the agent is limited by United States law to investigational use only and the agent should be kept out of reach of children.

6.7 Storage

The agent should be stored at a temperature of between 2° and 8° C. Participants transporting study medication from clinic to home will be provided with a cold, but unfrozen, ice pack. Participants will be instructed to store study medication in the refrigerator.

6.8 Registration/Randomization

CLO will be informed about the expected date and time of the scheduled screening visit as soon as it has been scheduled.

PID will be assigned sequentially to all participants who sign consent form at the PO and will designate the recruitment site, the study and the participant. Once a participant has signed a consent form and has satisfied all eligibility criteria:

- [contact]) or email ([contact]) the participant's eligibility checklist signed by Investigator and copy of the signed consent form to CLO during normal business hours (M-F 8:00 am – 4:00 pm Central Time).
- CLO will verify eligibility documents are complete and assign bottle numbers to dispense the study medication.
- CLO will email a confirmation of accrual to the study coordinator at the participating institution including the bottle numbers to be assigned to the participant. If a confirmation is not received within two hours, the coordinator should contact the CLO to confirm that eligibility documents were received.
- CLO will be responsible for tracking number of ER+ and ER- participants to ensure correct tracking of accrual. A notification of accrual will be sent to each PO after a participant has been assigned to treatment.
- After receiving the confirmation from CLO, this information should be conveyed to the local site investigational pharmacist to process the study drug request.

6.9 Blinding and Unblinding Methods

Not applicable

6.10 Agent Destruction/Disposal

DCP-supplied agents: at the completion of investigation, all unused study agent will be returned to NCI, DCP Repository according to the DCP "Guidelines for AGENT RETURNS" and using the DCP form "Return Drug List".

7. CLINICAL EVALUATIONS AND PROCEDURES

7.1 Schedule of Events

Evaluation/ Procedure	Screening Visit	Day 1	Day 7	Day 8 (± 1 Day)	Day before surgery (-2 Days)	Surgery Day 15-29	7 days after surgery (± 1 Day)	4-5 weeks after surgery
Informed consent	X							
Assess eligibility	X							
Medical history	X							
Physical exam	X					X		
Vital signs/ height and weight	X ¹		X ²	X ²	X ²	X ¹⁰		
Laboratory tests ³								
- CBC with differential								
- PTT, INR								
- CMP						X ⁴		
- TSH/FT3/FT4								
- HDL/LDL/Chol/TG								
- FSH ⁵								
Urine for PK	X					X		
Plasma for PK	X	X ⁶				X		
Immunogenicity sample	X ⁷					X ⁷		
Concomitant medications	X			X	X	X	X	X
Dispense study agent	X							
Study medication start		X						
Collect study agent						X		
Providing drug diary and instructions	X							
Provide Blood Pressure monitors	X							
Review agent diary/record						X		
Adverse events	X			X	X	X	X	X
Telephone contact				X	X		X	X
Tobacco and Alcohol assessments	X ⁸					X ⁹		

1. Participant will be given a BP monitor, instructed on its use, and given instructions on recording and reporting BP readings. See section 11.1.1 Reportable AEs, for how the blood pressure should be obtained.
2. Home BP check (morning) only. For Day 7 and Day 8, the readings should be approximately 24 hours apart. If the participant has missed taking their BP reading on Day 7 and Day 8 they should be encouraged to note two readings on the following days at least 24 hours apart from each other.
3. CBC with differential will include WBC, differential, platelets, hemoglobin and hematocrit. CMP will include electrolytes (Na, K, Cl, CO₂) glucose, BUN, creatinine, calcium, albumin, total bilirubin, AST, ALT, alkaline phosphatase.
4. Participant must be fasting for 10 hours for the surgery Day 15-29 lab collection.
5. FSH will be collected for confirmation of post-menopausal status at screening for women under 60 who are amenorrheic for 12 or more months.
6. For first 5 participants only, plasma PK samples will be collected 5 minutes and 2 hours after the first dose has been administered.
7. For participants 6-25.
8. Appendix D – administer the baseline version of tobacco and alcohol assessments

9. Appendix D – administer the follow-up version of tobacco and alcohol assessments
10. Blood pressure on Surgery Day 15-29 will only be obtained if the Day before Surgery average blood pressure is above Systolic ≥ 120 or Diastolic ≥ 80 .

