7.2 Baseline Testing/Prestudy Evaluation

7.2.1 Screening Visit (within 30 days of Day 1)

Newly diagnosed early stage breast cancer patients will be screened as potential participants from the University of Alabama at Birmingham, University of Wisconsin, University of Minnesota, University of Iowa, and Northwestern University. A history and physical examination will be performed as part of standard of care by providers at each institution.

The procedures to be performed to evaluate eligibility are:

- Invasive breast cancer or DCIS confirmed on pathology report; eligible participants must have invasive breast cancer between 0.5 cm and 5.0 cm in size based on imaging or for DCIS-only lesions, the imaging abnormality corresponding to the cancer must be at least 1.0 cm in size (i.e. calcifications, distortion or mass on mammogram, or mass or nonmass enhancement on MRI).
- Estrogen receptor status must be confirmed on pathology report. Estrogen receptor positivity defined as per 2010 ASCO-CAP Guidelines³⁶ – with at least 1% positive tumor nuclei in the sample on testing in the presence of expected reactivity of internal (normal epithelial elements) and external controls.
 - Eligible participants must have invasive breast cancer that is ER+ or ER-,
OR
 - Eligible participants must have DCIS that is ER+ and grade 3, or that is ER- and any grade.

*Beginning in November 2021, participants will be limited to estrogen receptor negative status.

- Her2neu status must be confirmed on pathology report for those with invasive cancer.³⁷ Her2neu status is defined as positive and negative based on the 2013 ASCO-CAP guideline. As recommended by the guideline, Her2neu equivocal results must have a reflex or new test to determine Her2neu status.
- Review of the participant's medical history.
- Measurement of height and weight.
- Evaluation of vital signs including temperature, pulse, blood pressure, and respiration rate.
 - For grade 1, grade 2, and non-persistent grade 3 hypertension, repeat blood pressure reading after 5 minutes.
 - If the average reading of the two measurements is grade 3 (systolic BP ≥ 160 mm Hg or diastolic BP ≥ 100 mm Hg) the patient is not eligible.
 - If the average reading of the two measurements is less than or equal to grade 2, then the participant is eligible.
 - If the average of the 2 readings is grade 1 or grade 2 hypertension, document the appropriate level hypertension on the baseline symptom form.

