- b. Once the lab results are obtained to determine eligibility, dispense the study agent in 3 bottles of 30 capsules of 80mg each and administer the first dose of 240mg (3 capsules) at the clinic visit after minimum of 2 hours post their last meal. The participant will be able to eat again after both PK blood draws are performed. This will be considered as Day 1.
- c. Document the date and time in the pill diary and provide the diary to participant with instructions on how to complete.
- d. First post-dose PK sample of 3mL blood will be collected within 5 minutes of drug administration.
- e. Second post-dose PK sample of 3 mL blood will be collected 2 hours from the time the drug was taken. Participants should not eat between the PK blood draws.
- f. The study dose has to be taken in the evening on empty stomach (2 hours after last eating and wait for 1 hour before eating again), every day until the day before surgery.
- g. They will be provided with a BP monitor to measure BP at home. While they are in clinic, they will be instructed on how to use the monitor. The instructions are noted on the BP diary for reference at home (Appendix C). Participants will be asked to measure and document the blood pressure values in the BP diary on Day 7, Day 8 (approximately 24 hours later) and day prior to surgery. All BP measurements should be taken in the morning. They will be instructed to notify the study team if the value of the reading is Systolic \geq 160 or Diastolic \geq 100 (grade 3). The study coordinator will contact the participants on Day 8 by telephone to assess adverse events and other symptoms, review medications and review the BP readings.

For participants 6 onwards:

- a. Review guidelines for agent administration with the participant and provide the diary to participant with instructions on how to complete.
- b. Dispense study agent – 9CUAB30 based on the dose of the study determined by interim analysis. Participant will be given enough study drug for the duration of participation in the treatment phase of the study.
 - Dose 240mg (3 capsules) – dispense 3 bottles of 30 capsules each or

- Dose 160mg (2 capsules) – dispense 2 bottles of 30 capsules each.
- c. Participants may start taking the medication in the evening on the date of dispense, in the evening on empty stomach (2 hours after last eating and wait for 1 hour before eating again) until the day before surgery.

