- Blood pressure monitor will be collected from participant and all the documented readings will be checked for grades and documented in the adverse event log accordingly.

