13.7 Evaluation of Toxicity

All participants will be evaluable for toxicity from the time of their first dose of 9cUAB30. The toxicity will be tabulated by severity with descriptive statistics.

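### Hypertension is graded from three home mornings against one screening occasion and only tabulated by severity, so the planned analysis will not separate a blood pressure change from the effect of reading more often

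*Combined protocol and SAP*

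**What the plan says.** **Baseline.** Section 7.2.1 lists "Evaluation of vital signs including temperature, pulse, blood pressure, and respiration rate" at the screening visit, within 30 days of Day 1. A raised value is repeated: "For grade 1, grade 2, and non-persistent grade 3 hypertension, repeat blood pressure reading after 5 minutes". The baseline grade is kept: "If the average of the 2 readings is grade 1 or grade 2 hypertension, document the appropriate level hypertension on the baseline symptom form". The Day 1 column of section 7.1 has no blood pressure entry.

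**On treatment.** Section 7.2.1: "Participants will be asked to measure and document the blood pressure values in the BP diary on Day 7, Day 8", and again on the day before surgery. Section 7.1, footnote 2: "Home BP check (morning) only. For Day 7 and Day 8, the readings should be approximately 24 hours apart". Footnote 10 and section 7.4.1 add a surgery-visit reading only where the day-before average reaches 120 systolic or 80 diastolic. Section 11.1.1 requires the study wrist monitor and one technique for all study readings, by staff and participants alike.

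**Use of the readings.** Sections 7.3.2 to 7.4.1 put the average of repeated readings in the database and use it to determine adverse events. Section 7.4.1 adds that "all the documented readings will be checked for grades and documented in the adverse event log accordingly".

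**Analysis.** Section 13.7: "The toxicity will be tabulated by severity with descriptive statistics". Section 13.5 adds a qualitative comparison with known retinoid toxicity. No summary of blood pressure change is planned. Section 13.1 describes a single-arm trial whose controls are archived tissue.

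**Phase I.** Section 6.2 reports that hypertension was more frequent at higher doses but that absolute readings did not rise. It infers that "participants entered the study with borderline hypertension and resultant repeated measurements led to sporadic BP elevations".

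**The concern.** A worst grade over several occasions is a maximum, and a maximum grows with the number of readings even when the underlying pressure does not move. Here the comparison is three scheduled occasions (four for women whose last home reading was raised) against one. Section 13.7 does not say whether the table is net of the grade already present at screening.

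The setting also moves from clinic to home when treatment starts, and no untreated group shows what the same schedule would produce without drug. A high hypertension count would then be open to two readings: a drug effect, or the measurement schedule. Section 6.2 met this problem in Phase I and resolved it by looking at change from baseline. The present plan keeps the summary that section 6.2 discounts and leaves out the one it relied on. Overall safety is a secondary objective (section 1.2.7), and hypertension is among the Phase I events that were more frequent at higher doses.

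**Working it through.** **1. Phase I figures (section 6.2, Table 3).** The hypertension percentages reproduce from the counts:

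| Dose (mg) | 0 | 20 | 40 | 80 | 160 | 240 |
|---|---|---|---|---|---|---|
| Events/n | 5/12 | 2/8 | 7/9 | 4/8 | 7/9 | 8/8 |
| % | 42 | 25 | 78 | 50 | 78 | 100 |

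240 mg against placebo, Fisher exact, two-sided: p = 0.015. Cochran-Armitage trend with mg scores: z = 3.05, p = 0.002. These tests are post hoc and unadjusted. The pattern is not monotone: 20 mg lies below placebo and 80 mg below 40 mg. Other events in the same table trend similarly: pruritus (0/12, 0/8, 0/9, 0/8, 1/9, 3/8) z = 3.37, p = 0.0008; the skin class (1/12, 1/8, 0/9, 3/8, 4/9, 4/8) z = 2.92, p = 0.004.

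**2. Three readings against one: simplest case.** If one occasion crosses the cut-off with probability p, independent occasions give P(any of three) = 1 − (1 − p)³:

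- p = 0.2: 1 − 0.8³ = 0.49
- p = 0.3: 1 − 0.7³ = 0.66
- p = 0.4: 1 − 0.6³ = 0.78

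**3. Allowing for correlation within a woman.** This is a simulation with no drug effect, using the plan's repeat-and-average rule at every occasion.

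- From the documents: 120 systolic as the repeat trigger, 160 as the grade 3 limit, exclusion at screening if grade 3, three scheduled occasions.
- Assumed, not in the documents: systolic only, mean 115-125 mmHg, between-person SD 12, within-person SD 6-10, grade 2 cut-off 140.

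Results:

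- grade 1 or above at screening: 32-62%
- grade 1 or above at the worst of three: 46-79%
- worse than baseline, worst of three: 20-41%
- worse than baseline, one on-treatment occasion: 10-22%

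Taking the worst of three thus about doubles the spurious worsening. With an assumed mean of 120-130 mmHg, separate runs gave 29-48% and 33-49% worse than baseline with no drug effect, so the overall range is about 20-49%. A true rise of 5 mmHg gave 47-65% in those runs. With an assumed clinic-to-home drop of 5 mmHg as well, it gave 32-50%, close to the no-effect range.

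**4. Precision of a paired mean change.** Half-width = t(0.975, n − 1) × SD/√n, with an assumed SD of change of 8-15 mmHg:

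- n = 36 (planned analysis size, section 13.1): 2.03 × 8/6 = 2.7; 2.03 × 15/6 = 5.1 mmHg
- n = 28 (after the 20% loss in section 13.3): 3.1 to 5.8 mmHg

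A mean of three readings, unlike their maximum, is not pushed upward by the number of readings.

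**5. Precision with a home pre-dose baseline.** The Schema limits enrolment from November 2021 to 12 ER-negative women, and the protocol version is dated January 2022, so at most about 12 women could supply this reading. With assumed day-to-day SD s, one baseline reading and the mean of three later ones, the variance of change is s²(1 + 1/3). At n = 12, t = 2.20:

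- s = 6: 2.20 × √(36 × 1.333/12) = 2.20 × 2.00 = 4.4 mmHg
- s = 10: 2.20 × √(100 × 1.333/12) = 2.20 × 3.33 = 7.3 mmHg

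**The case against.** The plan is more careful than a quick look at the schedule suggests. Device and technique are fixed (section 11.1.1), the repeat-and-average rule also applies at screening, the baseline grade is recorded, and averages go into the database. Blood pressure is not a named endpoint, safety is explicitly descriptive, and the home checks also serve monitoring through a notification threshold. All this stands. It means that a change from baseline can be calculated, not that one is planned.

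The simulation inputs are assumptions, and different choices move the percentages. That also stands: the direction is secure, the size is not.

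A home reading before dosing does not cure everything. Section 7.2.1 lets women start on the evening of dispensing, so for some that reading would be an evening one set against later mornings. It is still one occasion, there is still no control, and few women remain to be enrolled. It is therefore a supporting summary only.

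Three stronger readings are tempting:

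- A reader might infer that hypertension is the single clear dose-related signal from Phase I. Table 3 does not support this: pruritus and the skin class trend at similar strength, the hypertension pattern is not monotone, and section 6.2 reports no rise in absolute pressure over the first 24 hours or through day 36.
- A reader might infer that time of day changes together with treatment. The documents give no time for the screening reading. The 30-day gap is likewise a maximum: section 7.3.1 recommends starting once eligible, and the first five participants are dosed on the screening day.
- A reader might infer that drug and artefact can never be told apart. The stored averages argue against that.

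**Conclusion.** The point holds as a weakness of the planned analysis, not as evidence about the drug. Grades come from three or four on-treatment occasions against one at screening, and a severity table is the only planned summary. Reading frequency alone would make roughly 20-49% of women look worse than baseline. That range rests on the assumed pressures, SDs and grade 2 cut-off; the doubling from one occasion to three is the steadier result.

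A paired mean change removes the inflation from the number of readings and can be had to within about 2.7-5.1 mmHg at n = 36, if the SD of change is 8-15 mmHg. It does not remove the move from clinic to home or supply the missing control, so attribution to the drug would remain limited. Nor is a baseline on another device wholly excluded, since section 7.2.1 accepts outside physical examinations for confirming eligibility.

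**What to change.** 1. In section 13.7, beside the graded table, add the mean paired change in systolic and diastolic pressure with 95% CI for all treated participants with readings: the average of the scheduled Day 7, Day 8 and day-before-surgery values minus the screening value. Leave out the surgery-visit reading, which is taken only in women already raised and would bring selection into the average. This uses stored data and adds no participant burden.
2. For women still to enrol, add one home reading before the first dose, with the supplied monitor and the same five-minute repeat rule. Record its time, and take it in the morning where dosing does not start on the evening of dispensing. Report change from it as a supporting summary.

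**Cost.** One diary line and a short analysis. The home-baseline summary covers at most about 12 women, with a half-width of about 4.4-7.3 mmHg (assumed day-to-day SD 6-10). The report should state that setting and the lack of a control still limit attribution.
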